As this is a feasibility/pilot study, data from the study will be used to estimate effect sizes and inform a larger, randomized trial on the effects of the SinuSonic on individuals with compromised autonomic regulation, if warranted by the results.

Background: The SinuSonic was developed as a non-pharmaceutical device aimed to reduce nasal congestion via simultaneous administration of acoustic vibration and gentle oscillating expiratory pressure. Previous studies have demonstrated significant improvements in congestion and ease of breathing after immediate use of the device (Cairns & Bogan, 2019) and after twice daily use for 5-weeks (Soler et al., 2020). In this study, there was significant improvement in peak nasal inspiratory flow after only 2 weeks of use, and significant improvement in multiple self-report measures of congestion after 5 weeks of use. No adverse effects were reported. A review report by Schlosser, Salley and Soler likewise concluded that the device may improve pregnancy-related rhinitis, which may be particularly important for individuals who would prefer non-pharmacological interventions while pregnant or breastfeeding (<https://sinusonic.com/blogs/learn/pregnancy-rhinitis.>)

[figure not shown]
There are common clinical symptoms, such as anxiety and depression, that are frequently associated in individuals who feel unhealthy. The Polyvagal Theory (Porges, 1995, 1998, 2001, 2003, 2007) provides a model for which these psychological and physical symptoms may be viewed as the predictable consequences of a common neural substrate. This neural substrate involves the neural regulation of the heart and lungs, as well as neural regulation of the muscles of the face and head which function together as a Ventral Vagal Complex (VVC).

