The Eligibility Screening will consist of the following questions:

- 1) Are you between ages 18-99 years old? [YES TO QUALIFY]
- 2) Have you ever used the SinuSonic device? [NO TO QUALIFY]
- 3) Do you meet any of the conditions listed under the Safety and Warnings for use of the SinuSonic device? [NO TO QUALIFY]
 - a) Current or history of breathing problems (i.e., asthma, chronic obstructive pulmonary disorder (COPD), chronic bronchitis, emphysema, pneumonia, pleural effusion, lung cancer, cancer of the throat or upper airway)

- b) Current or history of circulatory problems (i.e., active nose bleed, heart arrhythmia, coronary artery disease, congestive heart failure, heart attack)
- c) Other conditions, specified as brain tumor, moderate to severe ear pain, fever greater than 101 degrees

- 4) Have you experienced symptoms of nasal congestion that have persisted at least 2 weeks? [YES TO QUALIFY]
- 5) Is your current level of nasal congestion at 5 or higher? (VAS included here) [YES TO QUALIFY]

Step 2: Consent/Linkage File

When all eligibility criteria are met, individuals will be invited to access the Informed Consent document (also provided via RedCap) to read and e-sign. Phone number and email address for the researcher will be provided in the event of questions or request for clarification.

After receiving the e-signed informed consent, researchers will assign a SubjectID number so that the participant can use the SubjectID number when completing all questionnaire assessment sessions using RedCap. Researchers will maintain a database linking SubjectID and name on their password-protected computers that will not be accessible to anyone who is not affiliated with the research.

Step 3: Pre-SinuSonic assessment

Participants will be asked to complete this assessment, via RedCap, prior to beginning use of the SinuSonic. Researchers will provide participants with a link to the assessment (text or email), along with their unique SubjectID number to use. The following instruments will be programmed into RedCap for completion:

Prior to SinuSonic Use (week 0):

- 1) Demographic Information Form
- 2) SF12 to assess overall health ("how you feel and how well you are able to do your usual activities")
- 3) TNSS to assess current nasal symptoms
- 4) BPQ to reflect perception of autonomic regulation
- 5) HADS to assess anxiety and depression
- 6) ATES to assess history of trauma/adverse events

Step 4: SinuSonic Use / Weekly assessments

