After completing the pre-SinuSonic assessment, researchers will inform participants to begin directed use of the SinuSonic (2 minutes per day, 2 times per day). Participants will be asked to confirm SinuSonic use on a weekly questionnaire. Additionally, participants will be asked to complete the following questionnaires approximately 5 minutes after final SinuSonic use for that week. The following instruments will be programmed into RedCap for completion:

Weekly, for 4 weeks (end of week 1, 2, 3, 4).

- 1) TNSS to assess current nasal symptoms
- 2) PGIC to reflect change in activity limitations, symptoms, emotions and overall quality of life

Step 5: Final research assessment

Participants will be asked to confirm use of the SinuSonic on a weekly questionnaire. Additionally, participants will be asked to complete the following questionnaires approximately 5 minutes after final SinuSonic use on the 5th consecutive week. The following instruments will be programmed into RedCap for completion:

End of Study (end of week 5).

- 1) TNSS to assess current nasal symptoms
- 2) PGIC to reflect change in activity limitations, symptoms, emotions and overall quality of life
- 3) BPQ to reflect perception of autonomic regulation
- 4) HADS to assess anxiety and depression

Description of Measures

Body Perception Questionnaire (BPQ) (Cabrera et al., 2018). The Body Perception Questionnaire (BPQ) is a self-report measure of body awareness and autonomic reactivity. Its items are based on the organization of the autonomic nervous system (ANS), a set of neural pathways connecting the brain and body. These pathways send information from the body about the status of organs and tissues (i.e., afferent projections). Some of these incoming signals form a basis for the subjective awareness of the body. The ANS also carries signals that control the functions of these organs and tissues (i.e., efferent projections). These signals can alter the functions of the body, depending on internal and external needs. Only the Autonomic Reactivity subscale will be distributed and used for the current study.

Hospital Anxiety and Depression Scale (HADS) (Zigmond & Snaith, 1983). HADS is a fourteen-item scale with seven items each for anxiety and depression subscales. Scoring for each item ranges from zero to three. A subscale score >8 denotes anxiety or depression.

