Short-Form Health Survey-12 (Ware et al., 1995). The SF-12 is a health-related quality-of-life questionnaire consisting of twelve questions that measure eight health domains to assess physical and mental health. Physical health-related domains include General Health (GH), Physical Functioning (PF), Role Physical (RP), and Body Pain (BP)

Total Nasal Symptom Score. The Total Nasal Symptom Score (TNSS) is the sum of scores for each of nasal congestion, sneezing, nasal itching, and rhinorrhea at each time point, using a four point scale (0–3), where 0 indicates no symptoms, a score of 1 for mild symptoms that are easily tolerable, 2 for awareness of symptoms which are bothersome but tolerable and 3 is reserved for severe symptoms that are hard to tolerate and interfere with daily activity. TNSS is calculated by adding the score for each of the symptoms to a total out of 12.

Adverse Traumatic Experiences Scale (ATES) (Kolacz et al., 2020). This measure asks about childhood adverse experiences, childhood maltreatment, other person maltreatment, life-threatening situations, sudden deaths of close ones, and personal health situations. Respondent-reported prior adverse events

of maltreatment, life-threatening situations, and sudden deaths of close ones are summed to create an adversity score (range: 0–19).

Patient Global Impression of Change (PGIC) (Hurst & Bolten (2004). The self-report measure Patient Global Impression of Change (PGIC) reflects a patient's belief about the efficacy of treatment. PGIC is a 7 point scale depicting a patient's rating of overall improvement. Patients rate their change as "very much improved," "much improved," "minimally improved," "no change," "minimally worse," "much worse," or "very much worse."

Data Analyses

Questionnaire data will be entered by participants into RedCap for researcher access. Researchers will export the data into SPSS for data analyses. All databases will be stored on password protected computers, accessible only to researchers affiliated with the study, and backed up on UNC servers.

As the current proposal is for a feasibility/pilot study, researchers will evaluate the following aims to determine whether a larger, randomized trial is warranted.

Aim 1: Examine associations between nasal congestion, autonomic functioning, adverse events, and mental health indices (depression, anxiety) at baseline. Pearson correlation analyses will be used to evaluate relationships among measures at each timepoint.

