Aim 2: (*These would be the aims for a future, randomized clinical trial, with preliminary testing using data from the current feasibility/pilot study*): Evaluate the effect of the SinuSonic on users with chronic nasal congestion. We will focus on three constructs important to psychological and physical health and hypothesize that:

- A) Nasal congestion will significantly improve when comparing baseline measures to follow-up measures at each week, and will maintain effects at 5 weeks. Repeated measures ANOVA will be used to evaluate mean change in outcome measures across time in PGIC and TNSS.
- B) Autonomic functioning will significantly improve when comparing baseline measures to end of study. Repeated measures ANOVA will be used to evaluate mean change in BPQ across time.
- C) Mental health indices (depression, anxiety) will significantly improve when comparing baseline measures to end of study. Repeated measures ANOVA will be used to evaluate mean change in HADS across time.

Aim 3: (*This would be an aim for a future, randomized clinical trial, with preliminary testing using data from the current feasibility/pilot study*). Evaluate the mediating effect of current/previous adverse experiences on outcome measures at 5 weeks, using regression models.

Aim 4: Calculate effect sizes for each outcome variable, which will be necessary to determine adequate sample size for a future clinical trial. G-Power software will be used to determine sample sizes based on the effect sizes of the current outcome measures.

References

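### The repeated measures ANOVA that Aim 2A assigns to PGIC cannot test improvement from baseline, because PGIC has no week-0 value and is already a rating of change

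*Combined protocol and SAP*

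**What the plan says.** The Aim 2A hypothesis (Data Analyses) reads: "Nasal congestion will significantly improve when comparing baseline measures to follow-up measures at each week, and will maintain effects at 5 weeks". The analysis given for it is one sentence covering two instruments: "Repeated measures ANOVA will be used to evaluate mean change in outcome measures across time in PGIC and TNSS".

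The two instruments follow different schedules (Data Collection Procedures):

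- **Step 3, week 0.** The list headed "Prior to SinuSonic Use (week 0" contains demographics, SF12, TNSS, BPQ, HADS and ATES. PGIC is not on it.
- **Steps 4 and 5, end of weeks 1 to 5.** Both TNSS ("TNSS to assess current nasal symptoms") and PGIC ("PGIC to reflect change in activity limitations, symptoms, emotions and overall quality of life") are completed.

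Description of Measures makes PGIC a seven-point scale of change. "Patients rate their change as" introduces seven categories running from very much improved, through no change, to very much worse.

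The plan gives no test of PGIC against 'no change', no responder definition and no numerical coding. Aim 4 asks the study to "Calculate effect sizes for each outcome variable, which will be necessary to determine adequate sample size for a future clinical trial" and does not say which analysis supplies the PGIC effect size.

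**The concern.** A time effect shows change from baseline only if baseline is one of the time points. For TNSS it is. For PGIC it is not, and it could not usefully be, because each rating already looks back and states a change. Running an ANOVA across those ratings asks whether the reported change itself changed between week 1 and week 5.

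The course that Aim 2A hopes for is prompt improvement that then holds. On PGIC that is a flat line on the improved side of the scale, which lies inside the null hypothesis of the planned test. A significant result, in turn, can come from benefit wearing off or from patients getting worse. Weekly means would show a reader the direction, but Aim 2A claims significant improvement and no inference on direction is planned for PGIC.

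A pilot whose purpose is to help decide on a randomized trial could therefore report no significant PGIC effect after a large stable benefit, or a significant one after deterioration.

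**Working it through.** The plan states no alpha, SD, correlation or expected effect for Aim 2A, so there is no figure of its own to reproduce.

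**Inputs from the documents.** n = 50, one group. PGIC occasions: weeks 1, 2, 3, 4 and 5, so k = 5. TNSS occasions: week 0 and weeks 1–5, so six.

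**Assumptions.** PGIC coded 1 (very much improved) to 7 (very much worse), with 4 = no change, each rating taken as change since week 0; complete data; two-sided alpha 0.05; SD 0.8, 1.0 or 1.5; within-person correlation ρ of 0.3, 0.6 or 0.8.

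**Step 1: the null hypothesis.** The time effect tests μ1 = μ2 = μ3 = μ4 = μ5, with k − 1 = 4 and (k − 1)(n − 1) = 4 × 49 = 196 degrees of freedom. The value 4 appears nowhere in this null. Any constant mean satisfies it, whatever the SD or correlation.

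**Step 2: the signal the test responds to.** With equal variances and correlations the noncentrality is λ = n Σ(μw − μ̄)² / [σ²(1 − ρ)].

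- Constant course at any level: every deviation is 0, so λ = 0.
- Straight-line shift of one point over five weeks: deviations ±0.5, ±0.25 and 0. The sum of squares is 0.25 + 0.0625 + 0 + 0.0625 + 0.25 = 0.625, and n times this is 50 × 0.625 = 31.25. At SD 1.0 and ρ = 0.3, λ = 31.25 / 0.7 = 44.6. At SD 1.5 and ρ = 0.3, λ = 31.25 / (2.25 × 0.7) = 19.8.

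The deviations are squared, so λ is the same for benefit accruing (4 to 3), benefit fading (3 to 4) and drift to worse (4 to 5).

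**Step 3: simulation.** Correlated normal ratings were rounded and clipped to 1–7. There were nine combinations of SD and ρ, with 2,000 replicates each.

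| Course of mean PGIC, weeks 1–5 | Time effect significant |
|---|---|
| No effect (4 throughout) | 4.3–5.3% |
| Stable benefit (2.5 throughout) | 4.2–5.8% |
| Stable worsening (5.5 throughout) | 4.2–5.4% |
| Accruing benefit (4.0 to 3.0) | 94–100% |
| Fading benefit (3.0 to 4.0) | 94–100% |
| Drift to worse (4.0 to 5.0) | 93–100% |

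A second run of the same grid agreed, apart from a highest no-effect value of 6.6% that did not recur.

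**Step 4: the comparison with 'no change'.** On the same data, a one-sample t-test of the week-5 rating against 4 detects stable benefit in 100% of runs. It rejects in 4.0–5.5% when benefit has faded to nothing by week 5, which is the right answer there.

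**Step 5: effect size from the time effect.** Median partial eta-squared for time is 0.016–0.018 under no effect and 0.016–0.017 under stable benefit. It is 0.10–0.44 under accruing benefit, fading benefit or drift to worse. It does not separate a large stable benefit from none.

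**The case against.** **The comparison across weeks is part of the hypothesis.** Aim 2A also claims that effects are maintained at 5 weeks, and differences among weeks 1–5 bear on that. This stands. The point is therefore confined to the improvement part. A non-significant time effect would still not prove maintenance.

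**The ANOVA also has an intercept.** It would test improvement if PGIC were coded with 'no change' as zero, but the plan specifies neither that coding nor that test. Averaged over weeks 1–5, it also rejects in 72–100% of runs under fading benefit although none is left at week 5.

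**It is a pilot and TNSS carries congestion.** This stands and limits the severity. Aim 2 is labelled preliminary testing, and PGIC is in any case a global rating covering activity, symptoms, emotions and quality of life.

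Four stronger readings are tempting and are not supported:

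- *Aim 4 will take its PGIC effect size from the ANOVA.* Aim 4 does not say so, and Aims 1 and 3 can also include PGIC. This is a possible consequence only.
- *The future trial will be mis-sized by entering single-arm change as a between-arm difference.* That is a separate question. It applies equally to TNSS, BPQ and HADS, and it does not arise from this test.
- *Weekly tests need a multiplicity correction with week 5 as primary.* Five unadjusted weekly tests give at least one false positive in 13–23% of no-effect runs, but that matters only if any single week counts as success. Aim 2A claims improvement at each week. If all five must succeed, all five favoured benefit in only 0–0.4% of no-effect runs.
- *The PGIC reference period is an error.* The documents do not say whether each rating looks back to week 0 or to the previous week. The RedCap item is not reproduced and may settle it.

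**Conclusion.** The point holds for the improvement part of Aim 2A as it applies to PGIC. The planned time effect cannot show improvement from baseline. That follows from the visit schedule and the definition of the scale, and does not depend on the simulation.

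The size is illustrative: about 4–6% rejection under any stable course, good or bad, and 93–100% when the mean moves by one point in either direction. These rates rest on n = 50 with complete data and on the assumed SD, correlation, alpha and coding.

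The TNSS analysis in the same sentence is not affected, and the comparison across weeks keeps a use in describing the course of PGIC. Severity is low to moderate.

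**What to change.** 1. In Aim 2A, separate the two instruments. Keep repeated measures ANOVA with week-0 contrasts for TNSS, and let those contrasts carry the congestion hypothesis.
2. Do not use the PGIC time effect as a test of improvement. Compare PGIC with 'no change' at each of weeks 1–5, including week 5, by a one-sample test (signed-rank or t) or as the proportion improved with a 95% CI. Report the weekly category distributions.
3. Use comparisons across weeks 1–5 only as evidence about the course over time, and describe PGIC as global change, not as a measure of nasal congestion.
4. If Aim 4 reports a PGIC effect size, do not take it from the ANOVA time effect. Express it against 'no change' and label it within-group change.
5. As a check, confirm which reference period the RedCap PGIC item uses and state it in the protocol. If it asks about the previous week, the week-5 rating should not be read as overall improvement.

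The cost is about one paragraph of analysis wording and a look at the RedCap item. If that item states no reference period, one participant-facing line would change. No new assessments are needed.

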Effects of SinuSonic on Psychological and Physical Well-Being

NCT number NCT06268730
Document Date 12/26/2023

Effect of the SinuSonic Device on Psychological and Physical Well-Being in Adults with Nasal/Sinus Congestion
PI (UNC): [name]

Brief background: Chronic nasal congestion impacts the functioning of the ventral vagal complex (VVC), which includes cranial nerves of the face and head (special visceral efferents), along with vagal regulation of the heart and lungs. Physiological compromise of the VVC due to a current or previous adverse experience may allow for worsening nasal congestion, which then has a circular impact back to poorer vagal regulation of the lungs.

This chronic cycle of congestion and poor vagal regulation can likewise impact mental health. Defensive symptoms/behaviors, such as anxiety and depression, are common emergent symptoms of a compromised VVC.

Purpose: The first aim of the study is to evaluate relationships between current/previous adverse events, degree of nasal congestion, perception of autonomic regulation and symptoms of anxiety and depression via self-report questionnaires.

The second aim of the study is to evaluate the effect of the SinuSonic on physical and psychological well-being in individuals with chronic nasal congestion. The SinuSonic is a self-applied nasal device designed to enhance physical well-being by reducing nasal congestion via simultaneous administration of acoustic vibration and gentle oscillating expiratory pressure. The vibration and expiratory pressure stimulate several cranial nerves that are included in the ventral vagal complex (VVC), including the cranial nerves of the face and head (special visceral efferents). According to the Polyvagal Theory (Porges, 1995, 1998, 2001, 2003, 2007), when the VVC is stimulated, the functioning of related cranial nerves and emergent behaviors should improve, supporting a calmer, more regulated nervous system, and improved mental health.

To evaluate the effects of the SinuSonic, self-report questionnaires will be administered (via RedCap) prior to beginning use of the SinuSonic, weekly during directed use of the SinuSonic (2 minutes per day, 2 times per day), and after 5 weeks of use of the SinuSonic. Weekly self-report questionnaires will include amount of SinuSonic usage and degree of nasal congestion. The final, 5-week questionnaires will include degree of nasal congestion, perception of autonomic regulation and symptoms of anxiety and depression.

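### Aim 2A, TNSS: repeated measures ANOVA with no missing-data rule would, as conventionally run in SPSS, drop a participant from every weekly contrast after one missed follow-up survey

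*Combined protocol and SAP*

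**What the plan says.** The combined protocol and SAP schedules TNSS before use (Step 3, week 0), at the end of weeks 1 to 4 (Step 4) and at the end of week 5 (Step 5). That makes six self-completed RedCap surveys. Step 4 has participants begin use only once the pre-use assessment is done, so week 0 is in effect gated and five surveys can be missed.

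Under Data Analyses, "Researchers will export the data into SPSS for data analyses". Aim 2A sets the hypothesis that "Nasal congestion will significantly improve when comparing baseline measures to follow-up measures at each week", and names the method: "Repeated measures ANOVA will be used to evaluate mean change in outcome measures across time in PGIC and TNSS". The SPSS procedure is not named. Missing surveys, drop-out, analysis sets, imputation and mixed models are not mentioned.

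Aim 4 will "Calculate effect sizes for each outcome variable, which will be necessary to determine adequate sample size for a future clinical trial". It does not say on which data set.

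**The concern.** Repeated measures ANOVA in its conventional SPSS form needs a complete row for each participant. One missed survey deletes that person's whole TNSS series, including the weeks that were answered. This works against Aim 2A, which wants a baseline comparison at each week: someone who answered weeks 1 to 4 and missed week 5 would not count in the week-1 contrast.

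If misses are unrelated to response, only precision is lost. If they are related, the people who remain are a selected group and the mean change is biased. It is overstated if non-improvers stop answering and understated if improvers do. If Aim 4 takes its TNSS effect size from this analysis, the error passes into the planning of the next trial, which is the pilot's stated purpose.

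**Working it through.** **Inputs.** From the documents: N = 50, one group, 1 + 4 + 1 = 6 TNSS surveys, five of which can be missed. The documents give no miss rate, SD, correlation or expected change, so there is no figure of theirs to reproduce. Assumed here: TNSS SD 2.5, correlation 0.6 between any two weeks, and a linear mean change to -1.0 at week 5 (so -0.20 at week 1).

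**Random misses.** Expected complete cases = 50 x (1 - m)^5, where m is the miss rate per follow-up survey. SD of change = sqrt(2 x 2.5^2 x (1 - 0.6)) = 2.236. SE = 2.236 / sqrt(n), with n = 50 x (1 - m) when all pairs for that week are used.

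| m | Complete cases of 50 | SE, complete cases | SE, all pairs that week |
|---|---|---|---|
| 3% | 42.9 | 0.34 | 0.32 |
| 5% | 38.7 | 0.36 | 0.32 |
| 10% | 29.5 | 0.41 | 0.33 |
| 15% | 22.2 | 0.48 | 0.34 |

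At 10%, about 5 x 50 x 0.90 = 225 follow-up scores would be received and about 5 x 29.5 = 148 used. There is no bias in this case.

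**Permanent drop-out related to observed response.** Weekly logit(p) = a + b x last observed change from baseline, with b = 0.25 (mild) or 0.5 (strong), negative when improvers leave, and a set to give the stated total drop-out. Complete-case week-5 change (truth -1.0):

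| Total drop-out | Non-improvers leave, mild / strong | Improvers leave, mild / strong |
|---|---|---|
| 20% | -1.11 / -1.20 | -0.88 / -0.79 |
| 27% | -1.15 / -1.28 | -0.85 / -0.71 |

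For week 1 (truth -0.20), from mild at 20% to strong at 27%, the complete-case estimate is about -0.33 to -0.56, or -0.06 to +0.16 in reverse. All week-1 pairs give about -0.2. A likelihood-based model on all observed scores (unstructured covariance) gives -0.97 to -1.02 at week 5 across 10, 20 and 27% drop-out, both slopes and both directions.

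**Skipped surveys related to observed response.** Here a participant may miss one week and answer again later, with 20 to 27% missing at least one survey. Complete-case week-5 change is -1.10 to -1.27, or -0.90 to -0.70 in reverse. Week 0-to-5 pairs give -1.02 to -1.07, or -0.98 to -0.90, and the model about -1.0. The part of the bias due to listwise deletion is (0.10 - 0.02)/0.10 = 80% to (0.27 - 0.07)/0.27 = 74%, or in reverse (0.10 - 0.02)/0.10 = 80% to (0.30 - 0.10)/0.30 = 67%. Root mean squared error falls from 0.37-0.46 (complete cases) to 0.30-0.34 (model).

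**Drop-out on the unobserved current score (20 to 27%).** Complete cases give -1.16 to -1.38 and the model -1.08 to -1.18. In reverse they give -0.84 to -0.57 and -0.92 to -0.79. The model removes about half the bias.

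**Effect size.** True d = 1.0/2.236 = 0.447. Complete-case d under response-related drop-out, mild at 20% to strong at 27%: 1.107/2.222 = 0.498 to 1.277/2.179 = 0.586, or in reverse 0.883/2.223 = 0.397 to 0.710/2.178 = 0.326. The shift is 0.05 to 0.14. The sampling SE of d with all 50 is sqrt(1/50 + 0.447^2/100) = 0.148 (95% CI 0.15 to 0.74). For scale only, n per arm = 2 x (2.80/d)^2 is 79 at the true d, 46 to 148 across these biased values, and about 29 to 660 across the sampling CI.

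**The case against.** The strongest objection is that the week-5 figures under permanent drop-out are not caused by the ANOVA. Everyone deleted there also lacks week 5, so a simple week 0-to-5 paired comparison has the same sample and the same bias. That stands. It does not stand for skipped surveys, where most of the week-5 bias comes from deleting people whose week-5 score exists, nor for the early weeks under either pattern.

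Second, the gain can be small. Under permanent drop-out, root mean squared error at week 5 is 0.33 for complete cases against 0.32 for the model (mild slope, 10%), 0.37 against 0.34 (mild, 20%) and 0.45 against 0.37 (strong, 27%). This is a pilot, and sampling error is large. That also stands, and it limits the severity. But a confidence interval shows sampling error and does not show selection.

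Third, the plan does not name the SPSS procedure, and the MIXED procedure would keep partial data. True: a reader might infer that the plan prescribes complete cases only, and it does not. The deletion follows from the usual form of the named method. Saying which form is meant is the remedy.

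A reader might also infer that non-improvers will drop out, so that benefit will be overstated. The documents do not show this. Step 4 times the weekly questionnaires "approximately 5 minutes after final SinuSonic use for that week", which might suggest that people who stop using the device are not surveyed. But "Weekly self-report questionnaires will include amount of SinuSonic usage and degree of nasal congestion" reads most naturally as a survey sent to everyone, including those reporting little use. Bias could go either way or be absent.

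Finally, the lack of a missing-data rule is study-wide. That is fair, but BPQ and HADS have only two time points, so listwise deletion there removes only people without week 0 or week 5.

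**Conclusion.** The point holds for TNSS in Aim 2A. The named method, as conventionally run, discards answered surveys and conflicts with the week-by-week aim. With random misses of 5 to 10% per survey the harm is precision alone: about 39 to 30 of 50 remain. If misses depend on observed response, the week-5 change is off by about 0.1 to 0.3 points in either direction, and the week-1 change by roughly as much, enough to alter its sign in the worst reversed case.

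These sizes rest on assumed miss rates, slopes, SD, correlation and a linear change. The effect-size shift of 0.05 to 0.14 does not exceed the sampling SE of 0.15. No missing-data method cures the uncontrolled pre-post comparison, so the mixed-model estimate should not be read as an unbiased device effect. The change should be made before the data are seen, but its absence is not fatal to a pilot.

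**What to change.** For TNSS, replace repeated measures ANOVA with a linear mixed model (SPSS MIXED) using all available surveys, with week 0 to 5 as a categorical factor and unstructured covariance, or a simpler structure if that does not converge. Report each week-minus-baseline contrast with a 95% CI and the number of surveys received each week.

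Take the Aim 4 TNSS effect from the model's week-5 contrast with its CI, and state the standardiser. On the assumptions above, dividing by the SD of change gives 1.0/2.236 = 0.447, and dividing by the SD of a single score gives 1.0/2.5 = 0.40.

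Add one shift sensitivity analysis, because the model removes only part of the bias if misses depend on unobserved scores. For example, move the missing week-5 scores 1 point up and then 1 point down; the week-5 change moves by the share missing x 1 point, so 0.20 to 0.27 with 20 to 27% missing. The 1-point size is a judgement: in the unobserved-score cases above, at most 0.8 was needed.

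PGIC has no baseline and stays outside this model.

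The cost is revised analysis wording and slightly more work in the same software, with no change to surveys or timing. When misses are random there is little week-5 precision gain over a week 0-to-5 paired comparison (SE about 0.33 for both at 10%). The simulations used maximum likelihood with unstructured covariance. They did not test convergence, interval coverage or a simpler covariance structure at N = 50.
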